8.4 Definitions of analysis sets

8.4.1 Enrolled Patients Data Set

The Enrolled Patients Data Set includes data collected from all patients who signed informed consent.

8.4.2 Lead-in Patients Data Set

The Lead-in Patients Data Set includes data collected from all patients who took at least one dose of lead-in medication.

8.4.3 Full Analysis set

The Full Analysis Set which will consist of all randomized patients who take at least one dose of double-blind study drug during the short term double-blind period and have a non-missing baseline value and at least one post-baseline efficacy value.

When the Full Analysis Set is used, patients will be presented in the treatment group to which they were randomized at the start of the short term double-blind treatment period (even if the treatment they received was different).

8.4.4 Per protocol analysis set

The per-protocol analysis set is a subset of the Full Analysis Set consisting of patients who do not violate the terms of the protocol which may affect the primary efficacy endpoint significantly. All decisions to exclude patients from the primary data set will be made prior to the un-blinding of the study.

Relevant Protocol Deviations (RPDs), used to determine complete or partial data exclusion for the short term double-blind treatment period due to prohibited concomitant treatment, are listed in section 7.7. Any further protocol deviations for a particular study will be specified in the study-specific SAP.

8.4.5 Safety analysis set

The Safety Analysis Data Set will consist of all patients who received at least one dose of double-blind study drug during the short term double-blind treatment period. The Safety Analysis Data Set will include any patient who accidentally received double-blind study drug but was not randomized in the study.

All analyses using the Safety Analysis Data Set will be presented by randomized treatment group, except in cases where information was available which indicated that a patient received a different treatment for the entire course of their participation in the double-blind treatment period of the study. In this case, the safety data for those patients will be presented by the treatment actually received. In case a patient never received the treatment as assigned by randomization, then the safety data for that patient will be presented by the first treatment received. No formal statistics analysis will be made for the safety variables, only descriptive summaries.

8.4.6 PD analysis set---Not Applicable

8.4.7 PRO analysis set---Not Applicable

8.5 Outcome measures for analyses

8.5.1 Primary outcome variables

- The primary outcome variable will be the change from baseline in HbA1c (% saxagliptin/dapagliflozin versus placebo only) at Week 24.
- Percent change from baseline in UACR at Week 24.

8.5.2 Secondary outcome variables

Secondary outcome variables for the Saxagliptin/Dapagliflozin treatment comparisons:

- Percent change from baseline in body weight (kg) at Week 24.
- Change from baseline in FPG (mg/dL) at Week 24.
- 30% reduction in UACR at Week 24.

- HbA1c < 7.0 % at Week 24.
- Change from baseline in seated SBP (mmHg) at Week 24.

Secondary outcome variables for the Dapagliflozin treatment comparisons:

- Percent change from baseline in body weight (kg) at Week 24.
- 30% reduction in UACR at Week 24.
- Change from baseline in seated SBP (mmHg) at Week 24.
- Change from baseline in HbA1c (%) at Week 24.
- Change from baseline in FPG (mg/dL) at Week 24.
- HbA1c < 7.0 % at Week 24.

8.5.3 Safety outcome variables

Safety outcome variables will be:

- Discontinuation for a sustained increase in serum creatinine by ≥ 1.5 times baseline level (AKI stage 1).
- AEs.
- Changes from baseline in SBP (mmHg), DBP (mmHg), and heart rate (bpm).
- Changes from baseline in clinical chemistry/haematology parameters.
- Changes from baseline in the findings from physical examination.
- Changes from baseline in clinical laboratory test results.
- Change from baseline in eGFR at Week 24.
- Change from baseline in eGFR at Week 27.

8.5.4 Exploratory outcome variables

CCI [REDACTED]

[REDACTED]

[REDACTED]

[REDACTED]

C
C
I

[Redacted text block containing multiple lines of blacked-out content, likely a list or table of data points.]

C [Redacted]
C [Redacted]
I [Redacted]
[Redacted]
[Redacted]
[Redacted]
[Redacted]
[Redacted]
[Redacted]
[Redacted]
[Redacted]

8.6 Methods for statistical analyses

Analyses on the variables shown below will only include measurements obtained prior to or on the date of rescue medication for some analyses. For other efficacy variables and exploratory variables, measurements after rescue medication will not be excluded from the analyses.

- Change from baseline in HbA1c (%)
- Change from baseline in FPG (mg/dL)
- Proportion of patients with HbA1c < 7%

C [Redacted]
C [Redacted]
I [Redacted]
[Redacted]
[Redacted]
[Redacted]

Further details will be specified in the Statistical Analysis Plan (SAP).

8.6.1 Analysis of the primary variable (s)

The analysis of the change in HbA1C from baseline to Week 24 will be based on a repeated measures model (RMM) including all scheduled time points following randomization up to and including week 24. The analysis of percent change from baseline in UACR from baseline to Week 24 will be conducted on the log-transformed UACR values using RMM. Separate RMM models will be used to compare saxagliptin/dapagliflozin with placebo, and to compare dapagliflozin 10 mg alone with placebo. RMM represent a longitudinal repeated measures analysis using ‘direct likelihood’, and include patients in the Full Analysis Set who have a baseline measurement and at least one post-baseline measurement. Analyses on HbA1c will only include measurements prior to the administration of rescue medication. Measurements made following rescue administration will not be included in HbA1c analysis.

The SAS procedure PROC MIXED will be used for primary analyses. The primary analysis models will each include the fixed categorical effects of treatment, week, randomization

stratification factor (i.e. anti-diabetic treatment strata) and treatment-by-week interaction as well as the continuous fixed covariates of baseline measurement and baseline measurement-by-week interaction. (In UACR analyses the natural logarithmic transformation will be applied to baseline UACR values prior to analysis.) An unstructured matrix for the within-patient error variance-covariance will be used. The denominator degrees of freedom will be calculated according to the Kenward-Roger method. A number of back-up models will be defined in the statistical analysis plan in case of non-convergence of the preferred model or other issues.

Point estimates and 95% confidence intervals for the mean change in HbA1c within each model for each treatment group as well as the difference in mean change between the saxagliptin/dapagliflozin treatment group and placebo will be calculated. P-value of the differences in Week 24 estimates between saxagliptin/ dapagliflozin and placebo will be calculated. For UACR, point estimates and 95% confidence intervals for the mean percent change in UACR within each treatment group will be obtained by exponentiation of model estimates, and differences in mean percent change will be similarly calculated. P-values of the differences in Week 24 percent change estimates between each treatment group (saxagliptin/dapagliflozin and, separately, dapagliflozin 10 mg only) and placebo from each model will be calculated.

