- d) Double-blind treatment period visits must be scheduled according to the randomization visit date (Day 1), with a protocol-allowed visit window of ± 5 days (except ±2 days for Visit 4). Subjects will bring their glucose meter and study supplies to the site at all visits. Once a patient is randomised, all visits should be scheduled relative to Visit 3. Any slippage in time from one visit must not accumulate to affect other visits.

- e) Randomized subjects discontinuing study medication or requiring rescue should have Week 24 procedures done at the time of rescue or study medication discontinuation. All subjects who discontinue study medication will be asked to continue ordinary visit schedule, unless they entirely withdraw consent from the study. In subjects discontinuing the study due to AE/SAE, the Investigator will follow the subjects until the event has resolved or stabilized. In addition, subjects who prematurely discontinue from the study may be contacted after discontinuation from the study, to collect vital status information.
- f) The start of enrolment is defined by the signature of the Protocol-Specific Informed Consent Form by the prospective subject. When only the Protocol-Specific Informed Consent is signed, and all other enrolment visit procedures are completed at a later time. The date on which the Informed Consent Form is signed will serve to determine the date and window for the entry into start lead-in /Day -28 visit (Visit 2).
- g) A brief physical examination should include cardiovascular, lungs, abdomen, and extremities; and any organ systems pertinent to the subject's signs, symptoms, or adverse events.
- h) A full physical examination should include general appearance, head, eyes, ears, nose, throat, neck, cardiovascular, lungs, abdomen, lymph nodes, extremities, neurological, skin, and musculoskeletal.
- i) Height only at Visit 1.
- j) Only HbA1c and s-Cr for eGFR calculation as well as single spot urine UACR (values at Visit 1).
- k) s-Cr for eGFR, standard lab and other IC/EC (values at Visit 2).
- l) Lab values from Visit 3 will only be used as baseline values for study entry and not for eligibility evaluating.
- m) The 12-lead ECG must be performed at Visit 2. The results from this ECG must be available, assessed, and initialled and dated by the Investigator prior to Visit 3.
- n) SAE should be collected from the time when the informed consent form is obtained from a patient

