4.3 Enrolment/screening period

Procedures will be performed according to the Study Plan Table 2.

At enrolment, obtain written informed consent prior to any study procedure or change in medical therapy required by the protocol. Consenting patients are assessed to ensure that they meet eligibility criteria. Patients who do not meet these criteria must not be enrolled in the study.

The below assessments to be performed for all consented patients at Visit 1:

- Contact IVRS/IWRS to obtain unique patient enrolment number
- Review and confirm the patient's eligibility for the study by assessing inclusion and exclusion criteria listed in Sections 3.1 and 3.2.
- A standard patient medical, medication and surgical history will be obtained with the review of selection criteria
- Record demography (including sex, age, race and ethnic group)
- Perform brief physical examination
- Obtain vital signs (seated BP and Heart Rate), body weight & height
- Obtain specimen (blood) for HbA1c, creatinine for eGFR calculation
- Obtain morning urine sample for UACR
- Perform urine pregnancy test for women of child bearing potential. Serum pregnancy test (β hCG) is performed, if urine pregnancy test result is positive.
- Review concomitant medications & Serious Adverse events
- Schedule the entry into lead-in visit between 06.00 a.m. and 10.00 a.m.
- Remind patient to be fasting and withhold anti-diabetic medications, insulin, antihypertensive drugs, lipid lowering drugs and anti-platelet drugs, the morning of their next visit and to refrain from tobacco/nicotine/ caffeine for 12 hours and alcohol for 24 hours, respectively prior to next visit

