4.4 Single-blind placebo lead-in period (Visit 2)

At visit 2, HbA1c and eGFR level from blood sample obtained from Visit 1 will be checked. If the HbA1c is ≥ 7.0 and $\leq 11.0\%$ and the eGFR value is within the range (20-80 mL/min/1.73 m²), then patients will enter a 4-week single-blind placebo lead-in period. At the lead-in visit, the patient's current dietary and life-style will be reviewed.

Patients will be instructed on diet and life-style in accordance with the local Diabetes guidelines or ADA guidelines by a qualified member of the study staff beginning with the lead-in visit. The below procedures will be performed during the visit for the eligible patients:

- Review and confirm the patient's eligibility for the study by assessing inclusion and exclusion criteria listed in Sections 3.1 and 3.2.
- Perform 12-lead ECG. ECG must be obtained and reviewed with no significant abnormalities prior to Randomization
- Obtain vital signs (seated BP and Heart Rate)
- Obtain blood samples for haematology and clinical chemistry
- Obtain specimens (blood) for creatinine for eGFR calculation, FPG and hepatitis screen panel
- Perform urine pregnancy test for women of child bearing potential. Serum pregnancy test (β hCG) is performed, if urine pregnancy test result is positive
- Have patient to take their first dose of lead-in period study drug
- Provide instruction on diet and life-style
- Dispense blood glucose meter and supplies, provide instruction on their use and selfmonitoring of blood glucose (see Section 5.2.6.1)
- Provide instruction on recording daily insulin and glucose values in the patient diary
- Dispense the study drug
- Obtain specimen for urinalysis
- Remind patient to bring study drug, diary and glucose meter to the next
- Schedule next visit
- Review concomitant medications and AEs including hypoglycaemic events
- Remind patient to be fasting and withhold the study medication, anti-diabetic medications, insulin, antihypertensive drugs, lipid lowering drugs and anti-platelet drugs, the morning of their next visit and to refrain from tobacco/nicotine/ caffeine for 12 hours and alcohol for 24 hours, respectively prior to next visit

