7.8 Post Study Access to Study Treatment---Not Applicable

8. STATISTICAL ANALYSES BY ASTRAZENECA

8.1 Statistical considerations

Multiplicity due to the two active treatment groups will be controlled by a Bonferroni adjustment, such that statistical significance will be determined according to a two-sided alpha level of 0.025. Within the saxagliptin 2.5 mg + dapagliflozin 10 mg treatment group the control of the alpha level in the testing of both co-primary endpoints (the percent change in urine albumin-to creatinine ratio (UACR) from baseline to 24 weeks and the change in HbA1c from baseline to 24 weeks) will require that each achieves statistical significance at the 0.025 level for a claim of superiority to placebo, and to proceed to a sequential comparison of secondary endpoints. Within the dapagliflozin 10 mg treatment group the control of the alpha level for the primary endpoint (the percent change in urine albumin-to creatinine ratio (UACR) from baseline to 24 weeks) will require the achievement of statistical significance at the 0.025 level for a claim of superiority to placebo, and to proceed to a sequential comparison of secondary endpoints. Parallel sequential testing strategies will be used for comparing each active treatment group to placebo for the secondary endpoints.

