8.2 Sample size estimate

With 142 subjects per treatment group with post-baseline measurements, there is 90% power to detect a difference of 0.42% in mean change from baseline in HbA1c between saxagliptin/dapagliflozin treatment group and placebo and, separately dapagliflozin treatment group and placebo at significance level of 0.025, using a two sided alpha and assuming a standard deviation (SD) of 1.0%. Assuming 5% of the subjects do not have a post-baseline assessment, a total of 450 subjects (150 subjects per treatment group) need to be randomized. The estimated sample size of 142 subjects per group will also yield 92% power to detect a 35% difference in UACR for each comparison at an alpha level of 0.025, assuming a SD = 80%. Based upon existing pooled data for dapagliflozin in treating patients with eGFR <60 ml/min/1.73 m² on ACEi/ARB the minimal detectable difference for this study is 0.27% for HbA1c and 21% for UACR

The significance level used to infer statistical significance for comparisons of primary and secondary endpoints will be 0.025, representing a two sided alpha level. Within the saxagliptin 2.5 mg + dapagliflozin 10 mg treatment group the control of the alpha level in the testing of both co-primary endpoints (the percent change in urine albumin-to creatinine ratio (UACR) from baseline to 24 weeks and the change in HbA1c from baseline to 24 weeks) will require that each achieves statistical significance at the 0.025 level for a claim of superiority to placebo, and to proceed to a sequential comparison of secondary endpoints. Within the dapagliflozin 10 mg treatment group the control of the alpha level for the primary endpoint (the percent change in urine albumin-to creatinine ratio (UACR) from baseline to 24 weeks) will require the achievement of statistical significance at the 0.025 level for a claim of superiority to placebo, and to proceed to a sequential comparison of secondary endpoints. Parallel sequential testing strategies will be used for comparing each active treatment group to placebo for the secondary endpoints. In all analyses p-values will be represent two-sided tests, and will not be adjusted for multiplicity.

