8.6.2 Analysis of the secondary variable(s)

Comparisons of the secondary efficacy endpoints between dapagliflozin 10 mg and placebo will be performed only if the test for the primary UACR endpoint is significant. Secondary efficacy endpoints will only be compared between saxagliptin/dapagliflozin and placebo will only be performed if each comparison of both co-primary endpoints is significant. If statistical significance is achieved as prescribed above, then the secondary endpoints will be compared between that treatment (those treatments) and placebo in the order specified in Section 2.2. A sequential testing procedure will be employed for secondary comparisons in order to control the type I error rate at the 0.025 level. Statistical comparisons between each treatment and placebo will be only performed for a given secondary endpoint if all previous sequential tests for that comparison are also significant. Otherwise, the testing procedure will stop at the secondary endpoint that does not reach statistical significance.

The secondary endpoints percent change from baseline in total body weight at Week 24, change from baseline in FPG at Week 24, change from baseline in seated SBP at Week 24, and change from baseline in HbA1c at Week 24 (Dapagliflozin 10 mg) will be analyzed by RMM analyses, as described for the primary analyses.

The secondary analyses of proportions for subjects with at least a 30 percent reduction in UACR from baseline to Week 24 and, separately, proportions for subjects with an HbA1c of less than 7 percent at Week 24 will be analyzed using a logistic regression model with adjustment for randomization strata and baseline measurement.

C
C

[REDACTED]

I

[REDACTED]

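### The efficacy models adjust for one baseline value only; adding the Visit 1 HbA1c and UACR already collected is an optional, cheap gain in precision, not the repair of an error

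*Protocol*

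**What the plan says.** Section 8.6.1 lists the terms of the primary repeated measures models: treatment, week, randomisation stratum, treatment-by-week, and the "continuous fixed covariates of baseline measurement and baseline measurement-by-week interaction". A separate model is fitted for each active arm against placebo. Section 8.6.2 states that body weight, FPG, seated SBP and, for the dapagliflozin arm, HbA1c "will be analyzed by RMM analyses, as described for the primary analyses".

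Footnote l to Table 2 (section 4.2) settles which visit supplies the laboratory baseline: "Lab values from Visit 3 will only be used as baseline values for study entry and not for eligibility evaluating".

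Earlier readings are scheduled. At Visit 1, section 4.3 has sites "Obtain specimen (blood) for HbA1c, creatinine for eGFR calculation" and collect a morning urine sample for UACR. Inclusion criteria 4 and 7 (section 3.1) require both results to lie in range. Weight and seated BP are also taken at Visit 1. At Visit 2, section 4.4 has sites "Obtain vital signs (seated BP and Heart Rate") and draw FPG. No visible text uses any of these earlier values in an efficacy model.

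**The concern.** A single baseline reading measures a patient's usual level with error. A second pre-randomisation reading of the same variable can carry further information about that level, and a model that ignores it may leave residual variance that the collected data could remove. The combination arm must win on both UACR and HbA1c before any secondary endpoint is tested, so precision on each matters for the whole sequence. The protocol itself names the covariates and defers only back-up models for non-convergence or other issues, so the choice is fixed here.

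**Working it through.** **Inputs from the protocol.** Section 8.1: "statistical significance will be determined according to a two-sided alpha level of 0.025". Section 8.2: 142 evaluable per group; "there is 90% power to detect a difference of 0.42% in mean change from baseline in HbA1c", "assuming a standard deviation (SD) of 1.0"%; 92% power for a 35% difference in UACR with SD 80%.

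**Reproducing the stated powers.** Power = Φ(d·√(n/2) − z), with n = 142, √71 = 8.426 and z = 2.241.
- HbA1c: d = 0.42/1.0; 0.42 × 8.426 − 2.241 = 1.298, power 90.3% (stated 90%).
- UACR: d = 0.35/0.80 = 0.4375; 0.4375 × 8.426 − 2.241 = 1.445, power 92.6% (stated 92%).
- UACR if 0.80 is a log-scale SD: d = −ln(0.65)/0.80 = 0.431/0.80 = 0.538; power 98.9%. The stated 92% therefore comes from 0.35/0.80.

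**Gain from adding Visit 1.** Let r13, r1y and r3y be the correlations of Visit 1 with Visit 3, Visit 1 with Week 24, and Visit 3 with Week 24. The residual variance is multiplied by 1 − p², where p = (r1y − r13·r3y)/√[(1 − r13²)(1 − r3y²)]. Power follows by dividing d by √(1 − p²). The protocol gives no correlations, so everything below is assumption. The stated SDs are taken as residual SDs of the model already adjusted for Visit 3.

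1. *Visit 1 adds nothing given Visit 3.* r13 = 0.8, r3y = 0.6, r1y = 0.48: p = 0, no gain.
2. *Correlation decays with time.* r13 = 0.8, r1y = 0.55, r3y = 0.6: p = 0.146, variance 2.1% lower. r13 = 0.85, r1y = r3y = 0.65: p = 0.244, variance 5.9% lower, HbA1c power 92.0%.
3. *Stable level plus noise, with the eligibility limits imposed on Visit 1 (simulation).* UACR has one void at Visit 1 and the mean of three at Visit 3 and Week 24.

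| Endpoint | Assumed SDs | Variance ratio | Power |
|---|---|---|---|
| UACR (patient / visit / void, log units) | 1.4 / 0.4 / 0.5 | 0.861 | 95.8% |
| | 1.2 / 0.5 / 0.5 | 0.866 | 95.7% |
| | 1.4 / 0.5 / 0.6 | 0.877 | 95.5% |
| | 1.2 / 0.3 / 0.7 | 0.897 | 95.1% |
| HbA1c (patient / visit, %) | 0.9 / 0.7 | 0.893 | 93.4% |
| | 0.8 / 0.6 | 0.881 | 93.7% |
| | 1.0 / 0.5 | 0.837 | 94.8% |

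4. *Between these, a level with slow drift and visit noise.* Variance fell 2–10% for UACR and 2–5% for HbA1c; other settings of this kind gave 5–8%.

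The variance reduction therefore spans about 0–14% for UACR (1 − 0.861) and 0–16% for HbA1c (1 − 0.837). A 5% reduction takes HbA1c power from 90.3% to 91.8%. On the log scale, even the largest UACR reduction takes power only from 98.9% to 99.6%.

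**Cost.** Each pairwise model has 2 × 142 = 284 patients. One useless slope per visit inflates the variance by about 1/274 = 0.4%; HbA1c power becomes 90.2% instead of 90.3%.

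**The case against.** The strongest objection is that this is a preference. The model is valid, it already adjusts for baseline, baseline-by-week and stratum, and it delivers its stated power. That stands, and it is why the point is optional.

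Several further objections also stand and limit the gain:
- Visit 3 UACR already rests on three first-morning voids (footnote r, section 5.1.1). Visit 1 UACR is a single void, truncated by eligibility.
- Visit 1 falls on Day −42 to −29, while the ACE inhibitor or ARB dose need be stable only for the 4 weeks before randomisation. A Visit 1 UACR may therefore precede a dose change. Diet advice and placebo also start only at Visit 2.
- If 1.0% and 80% are SDs of raw change and not residual SDs, the baseline-adjusted model starts from power at least as high, and the gain is generally smaller.
- Extra by-week slopes enlarge an unstructured model for which back-ups are already foreseen.

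A reader might infer that blood pressure gains most, since it is noisy and read twice before Visit 3. The documents do not support a figure. They give no SBP variance, the section on seated blood pressure is redacted, and footnote l fixes Visit 3 as baseline for laboratory values only. Visit 1 is also non-fasting, and the reminder to withhold antihypertensives is first given there, for the next visit.

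**Conclusion.** The point holds as an optional efficiency gain. Sections 8.6.1 and 8.6.2 use one baseline value where a second pre-randomisation reading of HbA1c and UACR exists in every correctly randomised patient. Adding it does not bias the treatment comparison and leaves the two-sided 0.025 level unchanged.

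The expected gain is modest: about 0–14% of residual variance for UACR and 0–16% for HbA1c, for HbA1c most plausibly single digits because correlation is likely to weaken over the 24 weeks. That is worth at most a few points of power, and under one point for UACR on the log scale. All of it depends on correlations that the protocol does not give, and zero lies within the range.

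A reader might infer that the trial is underpowered or the primary analysis deficient, or that precision is certain to improve at no cost. None of these follows: the stated powers reproduce, and there is a small price if Visit 1 proves uninformative.

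**What to change.** Before unblinding, add to the existing covariates:
- Visit 1 ln(UACR), with its by-week interaction, in both UACR models;
- Visit 1 HbA1c, with its by-week interaction, in the HbA1c models (co-primary for the combination arm, secondary for the dapagliflozin arm).

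Keep change from baseline defined on Visit 3. If wished, add Visit 2 SBP, Visit 1 weight and Visit 2 FPG to their own models in the same way, with a simple stated rule for a missing covariate. Visit 2 FPG is scheduled but is not an eligibility criterion, so a patient lacking it could otherwise drop out of the model. Leave the logistic models as they are: there an added covariate changes the conditional odds ratio being estimated, so the precision argument does not carry over directly.

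No new visit or sample is needed. The cost is a few degrees of freedom and slightly more model parameters, so the back-up models for non-convergence should state whether these terms are dropped first.
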